3.11.5 Multiple regression

To predict the value of the change in total LBM (kg), change in derived gait speed (m/sec) and change in total SPPB score based on a set of predictor variables, multiple regression analyses will be performed. Initially simple regressions will be performed, fitting one predictor at a time to gain an understanding of the relationship between predictor and outcome of interest. Then multiple regression using stepwise selection, will be performed fitting all predictor variables. The parameter estimates along with the 95% confidence limits by predictor will be produced. In addition, residual plots and goodness of fit measures will be evaluated, but not displayed in output. The SAS® procedures REG/GLM SELECT will be used. For purposes of an example, see the code below, just for the multiple regression of total SPPB score and the predictors: Total LBM [kg] [leg] and total fat body mass [kg] [leg]):

```
proc reg;
    model tsppb = tlbm_leg;
run;
proc reg;
    model tsppb = tfbm_leg;
run;
```

```
proc reg data=...;
```

```
model tsppb = tlbm_leg tfbm_leg / clb selection=stepwise(select=SL) stats=all;
plot rstudent*predicted;
output out=regd p=predict r=resid rstudent=rstudent;
run;
quit;

proc univariate data = regd noprint;
var rstudent;
histogram / normal;
probplot / normal (mu = est sigma = est);
run;
```

In view of the aforementioned regression analysis, it may be required to derive area under the curve, between a and b, $\int_b^a f(x)$, for some of the potentially associated factors of interest, which can be approximated by a sum of trapezoid areas, given by the following formula:

$$T_n = \frac{b-a}{2n} [f(x_0) + 2f(x_1) + 2f(x_2) + \dots + 2f(x_{n-1}) + f(x_n)]$$

Where n is the number of trapezoids, $x_0 = a$, $x_n = b$ and x_1 through x_n are the equally-spaced x-coordinates of the trapezoids 1 through n .

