2.14 Changes/Clarifications from the Planned Statistical Analysis in Protocol

The following changes/clarifications from analyses planned in the protocol include:

- Protocol amendment 3 states that for the Week 24 analyses treatment, visit, treatment date, region, baseline LBM and the two interaction terms treatment*visit and baseline LBM*visit will be included in the model. Instead a complete model will be used including two more interaction terms, region*visit and treatment date*visit. The motivation for including these is that both are randomization strata and important to be part of the model. This should also not cause any concerns in terms of convergence.
- Protocol amendment 3 states that the secondary variable is gait speed (sec). However, instead derived gait speed (m/sec) will be used in the analyses. It is the speed (m/sec) at which the 4-meter course is completed and is derived by dividing 4 meters (m) by the time (sec) to complete the course.
- Regression analyses (simple and multiple), which are not described in protocol amendment 3, will be included to evaluate potential exploratory factors affecting the patient outcomes.
- MCP-MOD: Hill coefficient for the sigmoidal Emax model changed from 2 to 3.5 as this better reflects the expected dose-response (as we are expecting the same efficacy of [placebo and bimagrumab 70 mg] and [bimagrumab 210 mg and 700 mg]). Guesstimates for all models were also included.
- Protocol amendment 4 states the inclusion of responder endpoints and logistic regression analysis related to this.
- Changes to subgroup and by-group presentations in of [Table 2.2](#) (see [Section 2.6](#) [Subgroups])

- Change to epoch presentation. Clarity in terms of the epochs per treatment and post-treatment versus analyses.

3 Clinical Study Report - Appendix 16.1.9 Documentation of statistical methods

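### SAP 3.11.5 reports ordinary 95% confidence limits after stepwise selection, so for predictors with no or weak effect the limits under-cover on average and the kept estimates are inflated

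*SAP*

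**What the plan says.** SAP 3.11.5 models change in total LBM, "change in derived gait speed (m/sec) and change in total SPPB score based on a set of predictor variables". It works in two steps. First: "Initially simple regressions will be performed, fitting one predictor at a time". The second step and its promised output read: "Then multiple regression using stepwise selection, will be performed fitting all predictor variables. The parameter estimates along with the 95% confidence limits by predictor" are to be produced.

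The example code asks for confidence limits (`clb`) in the same statement that selects on significance level: "model tsppb = tlbm_leg tfbm_leg / clb selection=stepwise(select=SL) stats=all". Diagnostics are limited: "residual plots and goodness of fit measures will be evaluated, but not displayed in output".

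For this analysis the visible text contains no entry or stay level, full predictor list, shrinkage, validation or post-selection adjustment. The only bootstrap in the SAP belongs to MCP-Mod (2.10.1.6, 1000 repeats).

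SAP 2.14 lists the regressions as an addition to the protocol analyses; they "will be included to evaluate potential exploratory factors affecting the patient outcomes".

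**The concern.** A predictor reaches the final stepwise table only if its estimate was large enough, relative to its standard error, in this sample. The ordinary 95% limit takes no account of that condition. Among predictors with little or no true effect, the ones that survive are those whose sampling error happened to be large. Their estimates are therefore too far from zero, and their limits miss the truth more than 5% of the time.

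What is at stake is how the exploratory results are read. The SAP's example relates SPPB to leg lean mass and leg fat mass, which bears on the protocol's working hypothesis (3.2) that more muscle mass leads to better function. A weak or chance association printed with a nominal 95% limit would look firmer and larger than the data support.

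**Working it through.** **Inputs from the documents.** About 245 patients randomized (SAP 2.13); about 200 expected to complete 24 weeks (protocol section 4), so n = 200; nominal 95% limits and a two-predictor example (SAP 3.11.5). The plan gives no figure for this analysis, so there is none to reproduce.

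**Assumptions not in the documents.** Entry level = stay level = s, with s = 0.05 or 0.15; 2, 5, 10 or 20 predictors; pairwise correlation 0.5 (2 predictors) or 0.3 (otherwise); residual SD 1; true slopes 0, 0.15 or 0.4 SD.

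**Step 1: one predictor with no effect.** It is kept if |Z| exceeds the two-sided cut-off for s, and its 95% interval covers zero if |Z| < 1.96. For s of at least 0.05,

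coverage given kept = (s − 0.05)/s = 1 − 0.05/s.

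- s = 0.15: 1 − 0.05/0.15 = 67%.
- s = 0.05: 1 − 0.05/0.05 = 0%. This holds by construction, since a null predictor kept at p < 0.05 must have an interval that excludes zero.

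**Step 2: one predictor with a real effect.** Let Z have mean λ and variance 1. Coverage is P(|Z − λ| < 1.96 given kept); inflation is E(Z given kept)/λ. For λ = 2 and s = 0.05:

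- P(kept) is about P(Z > 1.96) = 0.516.
- P(kept and covered) = P(1.96 < Z < 3.96) = 0.975 − 0.484 = 0.491.
- Coverage = 0.491/0.516 = 95%.
- E(Z given kept) is about 2 + 0.399/0.516 = 2.77, so inflation = 2.77/2 = 1.39.

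| λ | coverage, s = 0.05 | inflation | coverage, s = 0.15 | inflation |
|---|---|---|---|---|
| 1 | 84% | 2.45 | 90% | 2.01 |
| 2 | 95% | 1.39 | 97% | 1.24 |
| 3 | 97% | 1.09 | 97% | 1.04 |
| 4 | 97% | 1.01 | 96% | 1.00 |

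**Step 3: stepwise selection simulated, weak slopes plus nulls.** One true slope of 0.15 SD with 2 predictors and two with 5 or more; the rest null. There were 1500 runs for 2 predictors and 600 otherwise.

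| s | predictors | coverage, all kept | coverage, kept true slopes | inflation of kept true slopes | runs keeping at least one null |
|---|---|---|---|---|---|
| 0.05 | 2 | 82% | 94% | 1.37 | 8% |
| 0.05 | 5 | 77% | 91% | 1.45 | 18% |
| 0.05 | 10 | 62% | 90% | 1.47 | 38% |
| 0.05 | 20 | 46% | 90% | 1.50 | 60% |
| 0.15 | 2 | 87% | 96% | 1.26 | 17% |
| 0.15 | 5 | 85% | 95% | 1.27 | 37% |
| 0.15 | 10 | 75% | 93% | 1.32 | 70% |
| 0.15 | 20 | 64% | 92% | 1.35 | 95% |

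Most of the shortfall comes from kept null predictors, whose coverage in these runs is 0% at 0.05 and 51% to 55% at 0.15. For the weak true slopes the main effect is inflation.

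**Step 4: no true signal.** At least one null predictor is kept in 7% to 56% of runs at 0.05 and in 26% to 91% at 0.15, as the number of predictors goes from 2 to 20. Coverage of those kept is 0% and 47% to 57% respectively. The latter is below the 67% of step 1 because stepwise picks the most extreme of several candidates.

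**Step 5: strong slopes.** With two predictors, both 0.4 SD, coverage is about 95% and inflation 1.00 at either level.

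**Step 6: no selection.** Ordinary limits from the full model cover 94.3% to 95.4% in every simulated setting.

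**The case against.** Four points stand and set the limits of the concern.

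- **Role.** A reader might infer that the SAP will name the retained factors as drivers of outcome and carry them forward. The documents do not support that. SAP 2.14 speaks only of potential exploratory factors, and no test, dose choice or decision rule uses these models. They lie outside the primary MMRM (2.10.1.3) and the fixed sequence (2.10.2.3). The secondary MMRM separately fits fixation type, fall history and mobility aids as prespecified, unselected covariates.
- **Reach.** A reader might infer that every retained predictor has a wrong interval. Steps 2 and 5 show otherwise: strong predictors keep their coverage and are hardly inflated.
- **Visibility.** It is tempting to call the missing entry and stay levels and predictor list a defect. The public SAP has gaps in its efficacy sections where these could have stood, so nothing is claimed on that ground.
- **Mitigation.** The one-at-a-time regressions involve no selection, and the promise of estimates by predictor can be read as covering them too. A dropped factor may therefore still have an estimate, though one not adjusted for the other predictors.

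The code is also labelled an example, so it does not settle the final output. That does not remove the problem: the SAP's own prose joins stepwise selection to 95% limits.

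**Conclusion.** The concern holds as a minor point. Stepwise selection followed by unadjusted 95% limits gives, for predictors with no or weak effect, coverage below 95% on average and estimates too far from zero. In the weak-slope settings, coverage over kept predictors is about 46% to 87% and kept true slopes are inflated about 1.3 to 1.5 times. Those ranges rest on the assumed levels, predictor numbers, correlations and slopes above; the true size in this trial cannot be derived from the public text. The direction does not depend on the exact settings, but it fades as true effects become strong. No primary or multiplicity-controlled secondary conclusion is affected.

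**What to change.** In SAP 3.11.5, take the reported multiple-regression estimates and 95% limits from the prespecified model with all listed predictors and no selection. Show the stepwise result, if wanted, only as a ranking without limits.

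If the predictors are too many or too collinear for a full model, bootstrap the whole selection procedure (for example 1000 resamples, as already planned for MCP-Mod). Report how often each predictor is selected, with percentile intervals, and state how a predictor dropped in a resample is counted. This option was not simulated here, so no coverage figure is claimed for it.

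The first option is a short text change and a simpler procedure call; the second needs some added programming. Either way the intervals are wider and the table longer.

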3.1 Study design

This is a Phase IIa/IIb, 24-week, 4-treatment arms, parallel-group, randomized, double-blind, placebo-controlled, followed by a 24-week follow-up multi-center clinical study ([Figure 3-1](#)). The study consists of 3 epochs:

- A screening epoch of up to 6 weeks post-surgery will be used to assess eligibility.
- A treatment epoch of 24 weeks
- A post-treatment follow-up epoch of 24 weeks

[figure not shown]
At baseline visit, eligible patients will be randomized in a 2:1:2:2 ratio to either placebo, bimagrumab 70 mg, bimagrumab 210 mg, or bimagrumab 700 mg. Randomized patients will be treated for 24 weeks and will receive investigational treatment every 4 weeks for a total of 6 doses. When all patients have completed the Treatment epoch (Week 24), the primary analysis will be conducted to assess the effects of bimagrumab on primary and secondary endpoints including key safety measures. After completing the treatment epoch, patients will enter a follow up epoch with two visits at Week 36 and 48, the latter representing the End of study (EoS) visit. The final analysis will be performed when all patients have completed their EoS visit.

Patients randomized prior implementation of protocol amendment #2 were converted to fixed dose regimen at their next scheduled visit. Patients on 3mg/kg bimagrumab converted to 210 mg bimagrumab fixed dose and patients on 10 mg/kg bimagrumab converted to 700 mg

bimagrumab. Patients who are beyond their week 20 visit had their EoT at the next scheduled visit and continued the study as per protocol amendment #2.

Figure 3-1 Study design

There are 3 study epochs:

[figure not shown]
Screening epoch: Informed consent will be obtained prior to implementing any study specific procedures. The screening epoch begins as early as day 3 post surgery and ends with randomization no later than 42 days post-surgery (Study Day -39 to Day -1). The screening epoch should ideally start as soon as the patient starts to walk [REDACTED]

All entry criteria must be fulfilled before randomization (and latest on Day 42). This implies that any screening assessment can be repeated, as needed, if timelines to collect results allow this.

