It is recommended to perform simple screening assessments first (e.g. medical history, inclusion/exclusion criteria and vital signs) to identify non-eligible patients early, followed by the 4 meter gait speed test to demonstrate the ability to walk. Then, laboratory samples, which require shipping and analysis, should be collected along with the 12-lead ECG..

As soon as all inclusion criteria and none of the exclusion criteria have been met, the patient can be randomized.

The randomization date will be the 'Day 1' study visit (baseline/randomization) and used as reference for visit scheduling throughout the study period.

Treatment epoch: First dose of investigational treatment will be administered on the day of randomization (Day 1). Patients will receive 6 doses, one every 4 weeks. Final dose will be administered at the week 20 visit and the treatment epoch will end 4 weeks later at week 24, the EoT visit. Investigational treatment will be administered in addition to the local surgical standard of care for hip fracture [REDACTED]

Post treatment Follow-up epoch: After completing the End of Treatment visit, patients will enter a post-treatment follow-up with two visits at Week 36 and 48.

Following their study participation, patients will be further followed by their treating physician if required, according to the local standard of care.

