During the post-treatment follow up epoch, safety and efficacy assessments will continue until the EoS visit at week 48. .

[figure not shown]
[figure not shown]
[figure not shown]
[figure not shown]

Table 6-1 Assessment schedule

Study Epoch	Screening	Treatment							Post-treatment follow up		Notes
Visit name/study week	Screening / Day -39 to -1	BL/ Rand Day 1	Week 4	Week 8	Week 12	Week 16	Week 20	End of treatment / Week 24 *	Week 36	End of study / Week 48	
Days post-op or post 1st dose	D3 to 42 post- op	1	28	56	84	112	140	168	252	336	
Informed Consent	X										
Verify Inclusion/ Exclusion	X										
Randomization		X									
Demographics	X										
MMSE	S										Source documents only.
Hip fracture history	X										
Medical history	X										
Physical Examination	S				S			S		S	Source documents only.
Blood sample for serology	X										
Blood sample for hematology and chemistry	X		X	X	X			X		X	
Blood sample for hormones	X				X			X		X	
Urine sample	X		X	X	X			X		X	
Vital Signs	X	X	X	X	X	X	X	X	X	X	
Height	X										
Weight	X	X	X	X	X	X	X	X	X	X	
12-lead ECG (triplicate)	X	X			X			X			
Echocardiography								(X)		(X)	Only for patients enrolled

Study Epoch	Screening	Treatment							Post-treatment follow up		Notes
Visit name/study week	Screening / Day -39 to -1	BL/ Rand Day 1	Week 4	Week 8	Week 12	Week 16	Week 20	End of treatment / Week 24 *	Week 36	End of study / Week 48	
Days post-op or post 1 st dose	D3 to 42 post- op	1	28	56	84	112	140	168	252	336	
											before Amendment #3. W48 is to be performed only if W24 reading indicates clinically meaningful abnormality as per central reader's assessment.
Gait Speed	S										Source document only.
SPPB (incl. gait speed)		X	X	X	X	X	X	X	X	X	
DXA		X			X			X			All centrally read.
X-ray	X							X	(X)	(X)	At screening local X-ray taken during or after surgery is to be used. If bone union is incomplete at W24 per central reading, X-rays need to be performed until this is achieved at W36 and potentially W48 as well.
Drug administration		X	X	X	X	X	X				

Study Epoch	Screening	Treatment							Post-treatment follow up		Notes
Visit name/study week	Screening / Day -39 to -1	BL/ Rand Day 1	Week 4	Week 8	Week 12	Week 16	Week 20	End of treatment / Week 24 *	Week 36	End of study / Week 48	
Days post-op or post 1 st dose	D3 to 42 post- op	1	28	56	84	112	140	168	252	336	
AE/SAE reporting	To be recorded as needed										
Medications and medical procedures	To be recorded as needed										

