6.5.4.2 Clinical chemistry, [REDACTED] and muscle integrity markers

Clinical chemistry, [REDACTED] and muscle integrity marker assessments listed in [Table 6-3](#) will be conducted at the scheduled visits specified in this same [Table 6-3](#). [REDACTED]

Table 6-3 Clinical chemistry tests, [REDACTED] and muscle integrity markers

Clinical chemistry parameters measured at Screening, W4, W8, W12, W24 (EoT) and W48 (EoS)

Blood urea nitrogen (BUN)	Troponin I
Creatinine	Creatine kinase –MM
Calculated creatinine clearance	Creatine kinase –MB
Total bilirubin	Myoglobin
Aspartate aminotransferase (AST/SGOT)	Aldolase
Alanine aminotransferase (ALT/SGPT)	Fasting glucose
Gamma-glutamyltransferase (GGT/γGT)	HbA1c
Alkaline phosphatase	Cholesterol (total and HDL)
Total protein	Triglycerides
Albumin	Pre-albumin
Vitamin 25-hydroxy D	
High sensitivity C-reactive protein (hsCRP)	
Haptoglobin (if total bilirubin > 2ULN)	Amylase
	Lipase
Electrolytes (sodium, potassium, chloride, calcium, phosphorous, magnesium)	Uric acid
Activin A	estimated Glomerular Filtration Rate
Hormonal parameters measured at Screening, W12, W24 (EoT) and W48 (EoS)	
Sex hormone binding globulin (SHBG)	Luteinizing hormone (LH)
Estradiol	Follicle stimulating hormone (FSH)
Testosterone	Free thyroxine
	Thyroid stimulating hormone (TSH)

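### SAP 3.11.5 gives only the equal-interval trapezoid rule for AUC predictors, which misweights chemistry and any series that runs to Week 48

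*SAP*

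**What the plan says.** SAP 3.11.5 (Multiple regression) plans simple and then stepwise multiple regressions of the change in total LBM, gait speed and SPPB score on a set of predictors. It adds that "it may be required to derive area under the curve" "for some of the potentially associated factors of interest". The formula supplied is (b-a)/(2n) times [f(x0) + 2f(x1) + ... + 2f(x(n-1)) + f(xn)], where the points "are the equally-spaced x-coordinates of the trapezoids". The section does not name the factors, give a and b, or say whether levels or changes are integrated. Its code example uses leg lean mass and leg fat mass, both DXA measures.

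SAP 2.14 describes these regressions as an addition that "will be included to evaluate potential exploratory factors affecting the patient outcomes".

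The visit schedule is in Protocol Tables 6-1 and 6-3. SPPB, gait speed and weight are taken every 4 weeks from Day 1 to Week 24. After that, "patients will enter a post-treatment follow-up with two visits at Week 36 and 48" (Protocol 3.1). Chemistry is taken at screening and Weeks 4, 8, 12, 24 and 48, and hormones at screening and Weeks 12, 24 and 48. DXA is taken at Day 1 and Weeks 12 and 24.

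**The concern.** The formula gives every interval the same width, (b-a)/n. Where visits are denser early than late, the early part of the curve is overweighted and the late part underweighted. The size and sign of the error then depend on the shape of the curve. An AUC on such a schedule would not be the area that it is called, and patients whose curves differ in shape would carry different errors into the regression.

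The stake is the reading of exploratory results on which factors go with change in LBM, gait speed and SPPB. The primary test and the fixed sequence of secondary tests use no AUC.

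**Working it through.** The plan states no AUC value, so there is no figure of its own to reproduce. The check compares two formulas at nominal visit weeks.

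- SAP formula: h × [f0/2 + f1 + ... + f(n-1) + fn/2], with h = (b-a)/n.
- General trapezoid: the sum over intervals of (t[i+1]-t[i]) × (f[i]+f[i+1])/2.

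**Inputs.** Visit weeks come from Protocol Tables 6-1 and 6-3. Chemistry and hormones have a screening sample and no Day 1 sample, so placing their baseline at Week 0 is an assumption. The profiles are also assumptions: changes from baseline, scaled to a maximum of 1 and linear between visits, so that the general trapezoid gives the exact area.

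**Equal spacing, no error.**

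- DXA or hormones, 0 to 24 (h = 12), rise to Week 12 then flat: 12 × (1 + 0.5) = 18. True area 6 + 12 = 18.
- SPPB or gait speed, 0 to 24 (h = 4), linear rise to Week 24: 4 × (2.5 + 0.5) = 12. True area 24/2 = 12.

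**Unequal spacing.**

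| Series | h (weeks) | Assumed change profile | SAP formula | True area | Error |
|---|---|---|---|---|---|
| Chemistry 0-24 (0, 4, 8, 12, 24) | 24/4 = 6 | Rise to W12, flat to W24 | 6 × (1/3 + 2/3 + 1 + 0.5) = 15 | 6 + 12 = 18 | -16.7% |
| Chemistry 0-48 (adds 48) | 48/5 = 9.6 | Rise to W12, then flat | 9.6 × (1/3 + 2/3 + 1 + 1 + 0.5) = 33.6 | 6 + 36 = 42 | -20% |
| Hormones 0-48 (0, 12, 24, 48) | 48/3 = 16 | Rise to W24, then flat | 16 × (0.5 + 1 + 0.5) = 32 | 12 + 24 = 36 | -11.1% |
| Nine visits 0-48 | 48/8 = 6 | Rise to W24, then flat | 6 × (2.5 + 1 + 1 + 0.5) = 30 | 12 + 24 = 36 | -16.7% |
| Nine visits 0-48 | 6 | Rise to W12, flat to W24, back to 0 at W48 | 6 × (1/3 + 2/3 + 4 + 0.5) = 33 | 6 + 12 + 12 = 30 | +10% |

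**Mechanism on the nine-visit schedule.** The six intervals before Week 24 receive 36/48 = 75% of the weight; they cover 24/48 = 50% of the time. With A1 the area over Weeks 0-24 and A2 the area over Weeks 24-48, the formula returns 1.5 × A1 + 0.5 × A2. The relative error is 0.5 × (A1 - A2)/(A1 + A2). For the fourth row, 0.5 × (12 - 24)/36 = -16.7%. For non-negative profiles the error can lie anywhere from -50% to +50%, and a constant profile gives 0.

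**Levels instead of changes.** If SPPB itself is integrated, rising from an assumed 5.6 to 8.0 by Week 24 and then flat, the formula gives 5.6 × 48 + 2.4 × 30 = 340.8 against 5.6 × 48 + 2.4 × 36 = 355.2, about -4%.

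**Missed visits.** On the 4-weekly grid to Week 24 with Week 16 missing and a linear rise, h = 24/5 = 4.8. The formula gives 4.8 × (1/6 + 2/6 + 3/6 + 5/6 + 0.5) = 11.2 against 12, or -6.7%. A three-point series that loses its middle visit is left with one interval, where the two formulas agree.

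**Visit windows.** The windows in Protocol Section 6 are ±4 days at Week 12 and ±7 days at Week 24. For a DXA change that is flat from Week 12, visits at Days 88 and 161 give 161/4 × 3 = 120.75 against 44 + 73 = 117 (+3.2%). Visits at Days 80 and 175 give 131.25 against 40 + 95 = 135 (-2.8%).

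**The case against.** The strongest reply is that the plan may never apply the formula where it fails. The AUC is conditional, its factors and limits are open, and the only predictors shown in SAP 3.11.5 come from DXA, which is equally spaced. SPPB and gait speed appear there as outcomes, so the nine-visit example need not describe any predictor that will be used. The list of factors may also stand in parts of the SAP that are blacked out. All of this stands, and it is why the point concerns what the formula would do on a given schedule. It does not remove the point: weight shares the nine-visit schedule, chemistry is unequally spaced even to Week 24, and no other AUC rule is given.

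A reader might infer that AUC predictors will be wrong by -17% to +10%. The documents do not support that. The figures come from a few assumed shapes. A linear rise over 48 weeks on the nine-visit schedule gives -25%, a linear rise in chemistry to Week 48 gives -40%, and a constant profile gives 0.

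A reader might also infer that the ranking of predictors will be distorted. That has not been shown. If patients share one profile shape and differ only in size, every AUC is multiplied by the same constant, the slope rescales, and its t-statistic is unchanged. Distortion needs shapes that differ between patients, which is plausible but not quantified here.

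The integral sign appears with its limits reversed, but the text sets x0 = a and xn = b, so nothing follows from it.

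**Conclusion.** The point holds in a limited form. The only AUC rule in SAP 3.11.5 is exact at nominal times for DXA, and for hormones, SPPB and gait speed to Week 24. It gives a wrong area for chemistry, for hormones to Week 48, for anything on the nine-visit schedule to Week 48, and for the 4-weekly grid when an interior visit is missed. The illustrated errors are -17% for chemistry to Week 24, and -17% or +10% on nine visits to Week 48. They rest on assumed change profiles and, for laboratory values, on baseline placed at Week 0. They show order of magnitude and dependence on shape, and they do not bound the error.

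This is a minor point. The AUC is optional, the regressions are exploratory, and no primary or secondary conclusion depends on it.

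**What to change.** Replace the formula in SAP 3.11.5 with the sum, over consecutive available assessments, of (t[i+1]-t[i]) × (f[i]+f[i+1])/2 on actual study days. It agrees with the present formula wherever spacing is equal, so nothing is lost. State alongside it:

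- a common interval a to b for each factor;
- whether levels or changes from baseline are integrated;
- the day given to a baseline taken at screening;
- that a missed interior visit is bridged by the two neighbouring assessments;
- that the AUC is divided by the observed time span when follow-up is shorter than a to b.

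The last item matters because Protocol 5.5.9 brings patients who stop treatment back about 28 days after the last dose and then 4 weeks later, and Protocol Section 4 expects about 200 of 245 patients to complete Week 24 and about 120 to complete Week 48. Without time-averaging, a short series yields a small area simply because it is short. An average over a shorter span is still not the same quantity as one over the full interval, so those patients should be flagged in the output.

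The cost is a few lines of SAP text and code, with no change to data collection.
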